#### **Secondary outcomes**

1. Union rate via standard weight bearing plain radiographs ( harris axial/lateral views) at 6 weeks, 12 weeks, 6 months, 1 year, and 2 years after surgery. We will also obtain a 1X CT scan of the injured foot at 1 year after surgery to monitor for arthritic progression.
2. Radiographic parameters(Bohler's angle, clancaneal height/width/length, and angle of Gissan)
3. Other complications
4. Clinical outcomes will be evaluated to monitor patients' activity levels, pain, and functional status. This will be done primarily using the web-based Surgical Outcome System™ (SOS)
  - The SOS is currently a UCD IRB approved study (IRB # 1192222). It is a large international web-based registry that permits collection of baseline characteristics of patients undergoing orthopedic procedures. The data is collected using direct entry into a web-based collection system called the Surgical Outcome System (SOS). By completing these surveys, the investigator surgeon has the opportunity to monitor the subjects progress after treatment, even when they are not scheduled to see the provider. The investigator surgeon will also be able compare the outcomes to the average de-identified global data.
  - In order to utilize the web-based surveys, we would invite patients to dual enroll and consent into SOS. If, the subject forgoes SOS participation, the surveys may be filled out manually and this data will not be part of SOS.
  - Subjects fill out surveys before visits at 7 total time points: preoperatively, & postoperatively at 2, 6, and 12 weeks and 6 months, 1 and 2

**PROTOCOL TITLE:** Staged External Fixation of Acute Calcaneal Fractures

years. The surveys may include the Visual Analogue pain score(VAS), Patient-reported outcomes measurement information system 10 short form (PROMIS 10), or Veterans RAND 12 item Health survey (VR-12), Foot function index questionnaire (FFI-R) or Foot and Ankle Ability measure activities of daily living (FAAM ADL), and FAAM sport

**IV. Analysis:** The data will be analyzed for differences between splinting and external fixator treatment groups. Data will be stratified and analyzed for further differences in outcomes based on other factors (ie: demographics, comorbidities..)

- To assess significance the alpha level will be set at <0.05.
- Continuous data will be reported as means, standard deviation(SD), range, with 95% confidence intervals
- Categorical data will be reported as frequencies or percentages with 95% confidence intervals

**7) Data and/or Specimen Management and Confidentiality**

I understand that the UC Davis Health Electronic Health Record (EMR/EPIC) also contains the clinical data for Marshall Medical Center (MMC). I understand that MMC patient data cannot be accessed for research purposes and that I must take the necessary steps to ensure that MMC data is not accessed, used, or disclosed for UC Davis Health research purposes.

Since this is a prospective study, the PI/research team are part of the data collection process. Thus, the data will be identifiable at first to the research team. However, all efforts will be made to de-identify the data. A coding system will be used to assigned a unique code to each subject. Only authorized research staff members will have access to data.

All identifiable electronic data will be maintained on an encrypted device requiring password for access. Passwords will not be shared and will be protected from access.

If protected health information or personal information from the medical records will be stored on an encrypted device, investigators will follow applicable university policies (UC Davis Hospital Policy 1313, UCDHS P&P 2300-2499, and UC Business and Finance Bulletin on Information Security (IS-3).

All paper records will be stored in a locked room/file-cabinet with access limited to only individuals who have a right and need for access.

## 8) Data and/or Specimen Banking

If the patient also provides voluntary consent to enter the SOS web-based registry, the subject will be dual consented and also enrolled into the SOS. The data will enter the main SOS global registry(de-identified).

## 9) Provisions to Monitor the Data to Ensure the Safety of Subjects

This is a minimal risk study. There are no anticipated risks specific to study participation. There are no experimental procedures and participation in this study is not anticipated to affect the medical treatment of enrolled subjects.

Subjects will be randomized into two temporary treatments are likely to benefit from either arm of the study.

Procedures performed are currently standard of clinical practice for management calcaneal fractures.

In order to protect the rights and welfare of the subjects, an initial site set-up visit will be performed to ensure proper documentation. Further monitoring (including the close out visit) will take place as needed by our internal Research staff. The PI reviews and track all complications as standard care.

## 10) Withdrawal of Subjects

- Subjects can voluntarily withdraw at anytime
- Otherwise, the subjects are withdrawn if:
  - They have inadequate follow up without communicating with research staff.
  - Their health changes, and staying in the study is no longer in his or her best interest
  - They do not follow the study rules or no longer meet requirements to be in the study
  - The researchers terminate the study.

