#### **4) Inclusion and Exclusion Criteria**

Inclusion Criteria	Exclusion Criteria

• Voluntary consent

• Age 18 to 69

• Clinical and/or advanced imaging confirming an acute calcaneal fracture that has occurred within 2 days of which, eventually definitive surgery is recommended/accepted.

	

• unable to consent

• age <18

• Prior surgery of the affected extremity

• Prisoners

• Pregnant women

• Inflammatory arthritis

• Non-english speaking spatients

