## 5) Study Timelines

- Study will begin after IRB approval
- Patient recruitment will take place over two years, however this may be longer depending on the number of patients who require definitive surgery
- The duration of the subject's participation in the study will conclude at two year postoperatively
- The primary analysis will be complete within 3 years of the study start time

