### II. Methods

- Patients will be randomized to one of two treatment groups: temporary external fixation or temporary splinting. Both temporary treatments are those routinely used/available at the UCD health system. Subjects are to wear the temporary treatment method until definitive surgery.
- Safety endpoints occur at conclusion of the definitive fixation of their calcaneal fracture.

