### **III. Outcomes**

#### **Primary outcome**

1. Time to definitive surgery
2. Soft tissue complications (at routine follow ups which are 2, 6, & 12 weeks, and 6, 12, & 24 months after surgery)

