**15) Sharing of Results with Subjects**

Subjects will be aware of the survey scores as they are self-reported. Subjects will be aware of which treatment option they receive as they are visible. The results of this study will not be shared with other subjects or others.

**16) Prior Approvals:** IRB approval

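### Section 10 withdraws randomised patients for poor follow-up, a health change, not following study rules or lost eligibility, without saying that their outcomes are still collected, and no analysis set is named

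*Combined protocol and SAP*

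**What the plan says.** Section 10 lets subjects leave at any time. It then lists cases in which the researchers withdraw them. Two of these are "They have inadequate follow up without communicating with research staff" and "They do not follow the study rules or no longer meet requirements to be in the study". A third is a change in health that makes continued participation unwise for the patient, and a fourth is termination of the study. The list makes no exception for patients already randomised and says nothing about outcome data after withdrawal.

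The analysis paragraph (Section 6, IV) compares the two treatment groups, mentions stratification by other factors, sets alpha and lists descriptive summaries. It names no analysis set and gives no rule for withdrawn, crossed-over or never-operated patients.

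Four other places bear on the point:

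- **Visibility (Section 15):** "Subjects will be aware of which treatment option they receive as they are visible".
- **Timing:** the end of participation (Section 5: "participation in the study will conclude at two year postoperatively"), the safety endpoints (Section 6, II: "Safety endpoints occur at conclusion of the definitive fixation of their calcaneal fracture") and the second primary outcome (Section 6, III: "Soft tissue complications (at routine follow ups which are 2, 6, & 12 weeks, and 6, 12, & 24 months after surgery") are all counted from definitive surgery.
- **Treatment before surgery (Section 6, II):** "Subjects are to wear the temporary treatment method until definitive surgery".
- **Entry (Section 4):** a patient qualifies when "eventually definitive surgery is recommended/accepted".

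**The concern.** Randomisation makes the two groups comparable only if patients stay in the comparison whatever happens to them afterwards. Each withdrawal ground in Section 10 arises after randomisation, and each can depend on arm or outcome. A health change is the ground most directly tied to outcome. Poor follow-up acts on an endpoint that runs to 24 months. Acceptance of surgery can change after entry. If the study rules include wearing the assigned fixator or splint, adherence is to a visible treatment that differs by arm.

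A patient who is never operated on has no surgery time and no scheduled complication visit, because both are defined by the operation.

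If the patients lost differ between arms in number or kind, the bias can go either way. Losing patients who do badly with the fixator flatters external fixation. Losing slow splint patients makes splinting look faster. With no rule written down, whom to count would be decided after arm and outcome are known.

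**Working it through.** **1. The plan's own figure.** Section 6, I gives 35 per group and 30% dropout: 35/(1 − 0.30) = 50 per group, and 70/(1 − 0.30) = 100. This reproduces exactly. It keeps 35 evaluable patients per group, and so power. It does nothing to make those 35 comparable between arms.

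**2. Ceiling for complications.** Suppose all 15 of 50 allowed for in one arm gave no complication data, and 25% (assumed) of the 35 seen had a complication. That is 8.75 patients. The arm's rate then lies between 8.75/50 = 17.5% and (8.75 + 15)/50 = 47.5%, a width of 15/50 = 30 points. With 5 of 50 unknown the width is 10 points, and with 3 of 50 it is 6 points.

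**3. Bias and type I error for complications.** The documents give no complication rate and no loss pattern, so these inputs are assumed: true rate p = 25% in both arms, 50 per arm, pooled two-sided z-test at 0.05. Let w be the share lost, r the risk among the lost, f the share recovered from routine records at random, and u = w(1 − f) the share still missing. The rate seen is (p − u·r)/(1 − u).

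Example: 20% against 5% lost (fixator against splint), r = 50%, none recovered.

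- Fixator: (0.25 − 0.10)/0.80 = 18.75%.
- Splint: (0.25 − 0.025)/0.95 = 23.7%.
- False difference: −4.9 points.
- Pooled rate: (7.5 + 11.25)/(40 + 47.5) = 0.214.
- SE: √[0.214 × 0.786 × (1/40 + 1/47.5)] = 0.088.
- Ratio: 0.049/0.088 = 0.56.
- Type I error: Φ(−1.96 + 0.56) + Φ(−1.96 − 0.56) = 0.081 + 0.006, about 9%.

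Simulation agrees. Each cell gives the false difference in points, then type I error, rounded:

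| Lost, fixator / splint | Risk among lost | None recovered | One third | Two thirds |
|---|---|---|---|---|
| 6% / 6% | 25% | 0; 5% | 0; 5% | 0; 5% |
| 30% / 30% | 50% in both | 0; 5% | 0; 5% | 0; 5% |
| 6% / 2% | 50% | −1.1; 5% | −0.7; 5% | −0.3; 5% |
| 20% / 5% | 50% | −4.9; 9% | −3.0; 6% | −1.4; 5% |
| 20% / 5% | 75% | −9.9; 22% | −6.0; 11% | −2.7; 6% |
| 30% / 30% | 40% vs 20% | −8.6; 14% | −5.0; 8% | −2.2; 6% |

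The last row shows that equal numbers lost are not enough if the kind of patient lost differs.

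**4. Time to surgery.** This outcome is exposed only to withdrawal or non-operation before surgery. Assume equal lognormal times in both arms (median 12 days, log-SD 0.5), 50 per arm, and five per arm withdrawn before surgery but later operated on. A t-test on those remaining rejects:

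- 5% of the time if the losses are random in both arms;
- 9% if they are random in one arm and tend to be slow in the other;
- 26% if they are exactly the five slowest in the other arm, which is an extreme case.

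A rank test on all patients with the surgery dates kept rejects 5% in all three cases.

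**The case against.** Section 10 says only that subjects are withdrawn. A reader might infer that the plan stops outcome collection at that point or discards the data. The documents say neither, and the consent pages, which might address it, are not in the copy reviewed. What the text supports is that collection may stop.

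A reader might also take the 30% as a forecast of missing primary outcomes. It is a sizing allowance. The 30-point width needs every lost patient to contribute nothing, although complications are assessed at six visits and a patient lost at one year has already given several.

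The larger error rates come from assumed, strongly differential loss, while small or balanced loss does almost no harm. Surgery is recommended or accepted at entry, so non-operation may be uncommon. Reading the study rules to include wearing the temporary treatment is plausible, but the term is not defined. All of this stands, and it limits the size of the claim.

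It does not remove the claim. Outcomes come from routine visits (Section 6, II) and the investigator tracks complications (Section 9), but neither place says that this continues after withdrawal or feeds the analysis. Recovery is not assured either: patients who stop attending leave no routine-visit records, and the one-third and two-thirds shares above are assumptions.

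**Conclusion.** The point holds as a gap to close before data by arm are seen. Section 10 is directive, its grounds can be linked to a visible arm or to outcome, and nothing in the protocol retains the outcomes of withdrawn patients or says who is analysed. Enlarging enrolment does not repair this.

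The size is unknown from the documents. Under the assumed rates it runs from negligible (type I error near 5% when losses are small or alike in both arms) to a false 5 to 10 points and about 9% to 22% when 20% against 5% are lost at 50% to 75% risk. Recovering one third of the lost brings that to about 6% to 11%, and two thirds to about 5% to 6%. The 24-month complication outcome is the more exposed of the two primaries. The documents do not support a claim that bias will occur, or in which direction.

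**What to change.** 1. **Section 10.** Reword so that not following study rules, lost eligibility, a health change or missed visits does not by itself end outcome collection from routine records. Only withdrawal of consent or termination of the study ends it, and data to that point are kept. This concerns data only; treatment decisions are unchanged.
2. **Section 6, IV.** State that all randomised patients are analysed in the group assigned.
3. **Time to definitive surgery.** Keep the surgery date of withdrawn patients who are operated on, and report the number never operated on in each arm.
4. **Both primary outcomes.** Add a missing-data sensitivity analysis, such as a tipping point.

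I would not tie the repair to one test or a fixed cut-off day. Under the same assumed times, censoring lost patients at last contact and using a Gehan-Wilcoxon test still rejects about 8% to 14% when the five slowest in one arm are lost, and 6% to 8% when slow patients tend to be lost. It reduces informative loss without curing it.

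The cost is wording in two sections (and in the consent form if it says otherwise) and a little extra record review. The effect may be diluted by keeping non-adherent patients, and those who leave routine care may not be recoverable, which is why item 4 is needed.

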## 11) Risks to Subjects

There are no physical risks in this study.

There is the risk of randomization in this study.

There is a privacy risk, since we will record data which poses the risk of loss of confidentiality. The risk will be minimized through the processes described above. This study will abide by all applicable law, regulations, and standard

**PROTOCOL TITLE:** Staged External Fixation of Acute Calcaneal Fractures

operating governing the protection of human subjects, student information and protected health information.

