## PROTOCOL TITLE: Staged External Fixation of Acute Calcaneal Fractures

- All subjects will receive standard perioperative and operative treatment of their injury. Patients will receive standard clinical follow up for which their healing and functional status will be continually evaluated.
- Follow up after surgery will be at 6 time points: 2 weeks, 6 weeks, 12 weeks, 6 months, 1 year, 2 years
- The research related activities are randomization, using SOS surveys at specified time points, and collecting/reporting data regarding the outcomes from routine visits and survey responses.

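### The risk statements conflict with randomised assignment of the temporary treatment, and complications between randomisation and definitive surgery have no defined place in the primary comparison

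*Combined protocol and SAP*

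**What the plan says.** **On risk.** Section 11 states "There are no physical risks in this study" and then adds "There is the risk of randomization in this study" without saying what that risk is. Section 9 calls the study minimal risk and states "There are no anticipated risks specific to study participation" and that "participation in this study is not anticipated to affect the medical treatment of enrolled subjects". Section 18 relies on the minimal-risk status to set aside compensation for research injury.

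**On assignment.** Section 6, II. Methods: "Patients will be randomized to one of two treatment groups: temporary external fixation or temporary splinting". The assigned treatment is worn until definitive surgery, and both options are described as routine at the site. The same section says "The research related activities are randomization, using SOS surveys at specified time points", followed by data collection.

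**On complications.** Section 2 aims to show fewer soft tissue complications with external fixation and hypothesises a lower complication rate. In section 6, III. Outcomes, the primary soft tissue outcome is tied to six follow-up visits, all dated from surgery. Other complications are a secondary outcome with no definition or time window. Section 6, II. Methods adds "Safety endpoints occur at conclusion of the definitive fixation of their calcaneal fracture". Section 9 has the principal investigator follow every complication as part of usual care.

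**The concern.** There are two separate problems.

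First, randomisation here is an act of the study, and it settles which temporary treatment a patient receives. The plan cannot also say that participation leaves treatment unaffected and carries no physical risk, least of all when its hypothesis is that the two treatments differ in complication rates.

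Second, the randomised treatments are worn only before definitive surgery, but the primary complication outcome is observed only after it. A complication of the fixator or the splint that arises and settles before surgery has no scheduled place in the primary comparison. The same is true of a patient who never reaches definitive surgery, or who is withdrawn beforehand under section 10 because of a change in health: that patient has no postoperative visit. A claim of fewer complications would then describe only part of the period in which the treatments can cause them.

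**Working it through.** **Step 1. The risk statements set beside the design.**

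| Statement | Section | Compared with section 6, II. Methods |
|---|---|---|
| Participation not anticipated to affect treatment | 9 | Conflicts: randomisation is a research activity and sets the temporary treatment |
| No risks specific to participation | 9 | Conflicts: a patient may receive, because of the study, a treatment he or she would not otherwise have had |
| No physical risks | 11 | Conflicts: each arm is a physical treatment, and section 2 expects complication rates to differ |
| A risk of randomisation | 11 | Consistent with the design, but its content is not described |

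**Step 2. Where a complication before surgery could be counted.**

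- Primary soft tissue outcome: no, unless the event is still present at a postoperative visit, the first being at 2 weeks.
- Secondary outcome for other complications: possibly, since no time window is given. It also has no definition.
- Safety endpoint sentence: unclear. It may mean one assessment at the end of definitive fixation, or a safety period that ends there. The second reading would cover the temporary treatment.
- Investigator's tracking in section 9: yes for clinical oversight, but no by-arm reporting is specified.

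The events are therefore not excluded from the plan, but nothing defines or schedules them for comparison.

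**Step 3. Number of patients exposed.** Section 6, I. Design gives 35 per group, 70 in total, and 30% dropout. 70 / (1 - 0.30) = 100 and 35 / 0.70 = 50, which match the stated 100 patients and 50 per group. The 35 itself cannot be rederived, because no effect size, SD or event rate is given. This point does not depend on it.

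**Step 4. How many events might be involved.** The documents give no rate, so the rates p below are assumptions. Expected events in an arm of 50 are 50 x p, and the chance of at least one is 1 - (1 - p)^50.

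| Assumed p | Expected events | Chance of at least one |
|---|---|---|
| 2% | 1 | 64% |
| 5% | 2.5 | 92% |
| 10% | 5 | 99% |
| 20% | 10 | >99.9% |

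**Step 5. What counting them could do to the comparison.** Assume postoperative complication rates of 25% (splint) and 10% (fixator), and independent pre-surgical rates s (splint) and h (fixator). The rates from randomisation onward are 1 - 0.75 x (1 - s) and 1 - 0.90 x (1 - h).

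| h | s | Fixator | Splint | Splint minus fixator |
|---|---|---|---|---|
| 0% | 0% | 10% | 25% | 15 points |
| 5% | 0% | 14.5% | 25% | 10.5 points |
| 10% | 0% | 19% | 25% | 6 points |
| 20% | 0% | 28% | 25% | -3 points |
| 10% | 10% | 19% | 32.5% | 13.5 points |
| 0% | 10% | 10% | 32.5% | 22.5 points |

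Depending on which arm has the pre-surgical events, the difference shrinks, reverses, barely moves or grows.

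**The case against.** The strongest defence is that both temporary treatments are routine at the site, so the risks belong to the injury and its usual care rather than to the study. This may explain the minimal-risk wording, and some patients in the fixator arm might have had a fixator anyway. It does not remove the conflict, because randomisation can still give a patient the option that he or she would not otherwise have received.

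Several stronger readings are tempting, but the documents do not support them:

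- *Device harms fall outside safety monitoring.* Section 9 has the investigator follow all complications with no period excluded, and the safety endpoint sentence may describe a period that includes the temporary treatment.
- *Pre-surgical harms have no planned comparison at all.* The secondary outcome for other complications has no time window, and section 6, IV. Analysis compares the groups. What stands is that this outcome is undefined.
- *The minimal-risk claim is the reason for light monitoring.* Section 9 states no such link. The gap before surgery comes from the timing of the outcomes in section 6.
- *Participants are given a false statement.* The consent text is not available for review.
- *The omission favours external fixation.* Splint-related events would be omitted too, so the direction is not known.
- *The one-year CT scan is an undeclared research risk.* The plan says "We will also obtain a 1X CT scan of the injured foot at 1 year after surgery to monitor for arthritic progression", but does not list it among the research activities or say whether it is routine.

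**Conclusion.** The point holds in two parts. The risk statements in sections 9 and 11 contradict the randomised assignment in section 6 and must be reconciled; this rests on the text alone and needs no assumption. In addition, the primary soft tissue outcome, followed as written, omits complications that arise and resolve between randomisation and definitive surgery, and no other outcome defines or schedules them.

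The size of the second part cannot be fixed from the documents. Up to about 50 patients per arm are exposed. Under the assumed rates of 2% to 20%, 1 to 10 events per arm are at issue, and a 15-point postoperative difference could become anything from -3 to 22.5 points in the cases shown. These figures show that the window can matter. They do not show that it biases the trial in a particular direction.

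**What to change.** 1. Reconcile sections 9 and 11 with section 6, II. Methods: state that the study sets the temporary treatment and that each arm carries its own physical risks. Check section 18, which relies on the minimal-risk status.
2. In section 6, III. Outcomes, count soft tissue and device-related complications from randomisation onward in both arms, with a definition.
3. Add one table by arm for randomisation to definitive surgery, including patients who never reach surgery. The source can be the complication review that the investigator already does, so no new visit is needed.
4. State whether the safety endpoint sentence marks a single assessment or the end of a safety period.

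The cost is a protocol amendment and one more table. The ethics board may also wish to look again at the minimal-risk classification.
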